### **12.3.2 Medication and Non-Drug Therapy**

All medications, including non-steroidal antirheumatic drugs, vitamins and minerals for therapeutic use, taken for up to 2 weeks prior to the booster vaccination until the blood draw 21 – 35 days after the booster will be documented in the subject's clinic / hospital and study records using the guidelines set forth by the Sponsor.

The following concomitant medication will be documented in the CRF:

- medication to treat fever or pain after vaccination;
- medication possibly interfering with the immune response (e.g., systemic corticosteroids);
- medication to treat SAEs;

including product name (generic name), total daily dose as well as start and end date of treatment.

Medication to treat SAEs will also be reported to the Sponsor on SAE reports as described in Section [12.2.9](#).

Any vaccinations given during the entire study period must be documented in the CRF.

In the context of this study, information on non-drug therapy will only be collected in relation to SAEs.

## 12.4 Physical Examinations

At enrollment and subsequent study visits (as described in Section 10.3), a physical examination will be performed on the following body systems being described as normal or abnormal: general appearance, head and neck, eyes and ears, nose and throat, chest, lungs, heart, abdomen, extremities and joints, lymph nodes, skin, and neurological. At the yearly blood draw visits (as described in Section 10.3.2.1) and at the Booster Vaccination Visit (Visit 4) (as described in Section 10.3.2.2), if significant medical events (e.g. events fulfilling SAE criteria) are detected, the condition will be described on the medical history CRF. At the Post-booster Visit (Visit 5), if a new abnormal or worsened abnormal pre-existing condition is detected, the condition will be described on the AE CRF.

## 12.5 Clinical Laboratory Parameters

Apart from urinary pregnancy testing, no safety laboratory testing will be conducted in this study.

### 12.5.1 Assessment of Abnormal Laboratory Values

In the event of laboratory tests being required for any reason, the Investigator must assess the clinical significance of all abnormal laboratory values as defined by the compendium of normal values for the reference laboratory. The Investigator's assessment of each abnormal laboratory value is to be recorded in the subject's medical records. For each abnormal laboratory value determined between the second booster vaccination and the Post-booster Visit, the Investigator will assess whether the value is also considered an AE (see definition in Section 12.2). If yes, the sign, symptom, or medical diagnosis (including the abnormal laboratory value) will be recorded on the AE CRF.

## 12.6 Vital Signs

Vital signs will include height (cm), weight (kg), body temperature (°C), pulse rate (beats/min), and systolic and diastolic blood pressure (mmHg). Weight and height will be measured at the yearly blood draw visits. Body temperature will be measured at the Booster Vaccination Visit (Visit 4) before administration of the vaccine. Blood pressure and pulse rate will be measured before the booster vaccination at the Booster Vaccination Visit (Visit 4) and at the Post-booster Visit (Visit 5), when subjects are in the sitting position. At the Booster Vaccination Visit (Visits 4) pulse rate will also be measured 30 minutes after administration of IP.

Vital sign values are to be recorded on the physical examination CRF. For each vital sign value, the Investigator will determine whether the value is considered an AE (see definition in Section 12.2). If assessed as an AE, the medical diagnosis (preferably), symptom, or sign, will be recorded on the AE CRF. Additional tests and other evaluations required to establish the significance or etiology of an abnormal result, or to monitor the course of an AE should be obtained when clinically indicated. Any abnormal value that persists should be followed at the discretion of the Investigator.

## **12.7 Responsibilities of the DMC**

An independent DMC will be utilized for this study. The DMC will consist of 3 individuals who will be selected based upon their knowledge in clinical medicine and their expertise and understanding of TBE vaccines, clinical research and/or skills. A meeting of the DMC may be called at the discretion of the Sponsor, e.g., to address any safety concerns arising during the conduct of the study.

### **12.7.1 Responsibilities of the DMC**

- Upon Sponsor's request, provides independent monitoring of safety issues, which means it reviews and evaluates all SAE reports and study discontinuations for: (i) increases in frequency of SAEs and study discontinuations within the study; and (ii) increases in frequency of SAEs and study discontinuations across studies with the same preparation; and (iii) SAEs in the study sample compared with the population based on what is known from the literature;
- Reviews data produced from the study upon the Sponsor's request to determine whether the conditions on which study design is based have remained the same or have changed. If changed, the DMC will determine whether or not the changes mandate changes to the protocol and suggest a protocol amendment;
- Upon the Sponsor's request, meets for discussion and gives recommendations to the Sponsor as to whether the study should progress unchanged, or the study requires changes, or the study should be terminated prematurely. Pfizer will forward such decisions, which may include summaries of aggregate analyses of endpoint events and of safety data that are not endpoints, to regulatory authorities, as appropriate;
- Can propose an unplanned safety analysis of clinical trial data.

## 13. STATISTICS

The immunogenicity analysis of the ELISA and NT results obtained 38, 46, 58, 70, 82, 94, 106 and 118 months after the first booster vaccination may be carried out separately as soon as the relevant data become available. A final clinical study report including all data will be prepared after completion of the study.

### 13.1 Sample Size and Power Calculations

A total of 202 subjects who were administered the first booster vaccination in Study 700401 at 3 or 4 years after the third vaccination in Study 209 will be invited to participate in this study. Of these, approximately 175 study participants are expected to return and to provide information on antibody persistence after the first booster vaccination with either FSME-IMMUN 0.25 ml Junior or FSME-IMMUN 0.5 ml. With this sample size, the 95% confidence interval of the seropositivity rate will extend no more than 5.8% from the observed rate assuming the observed rate lies in the region of 90%.

### 13.2 Datasets and Analysis Cohorts

Per-protocol dataset: Subjects will be included in the “per protocol” dataset if they

- fulfill inclusion/exclusion criteria
- have no major protocol violations
- have available serology data

Modified intent to treat dataset: Subjects will be included in the modified “intent to treat” analysis if they

- have available serology data

### 13.3 Handling of Missing, Unused, and Spurious Data

Only subjects with available data will be included in the statistical analysis. Missing values for antibody titer at 38 and 46 months will neither be replaced nor estimated. Any missing values at later time points (i.e. 58, 70, 82, 94, 106 and 118 months) will be estimated if at least three data points are available, assuming an exponential decline in antibody titers in time.

## 13.4 Methods of Analysis

### 13.4.1 Primary Endpoint

Point estimates and 95% confidence intervals for the seropositivity rate at each time point when blood is drawn (from approximately 38 months to 118 months after the booster vaccination in Study 700401, and separately after the booster vaccination) in this study as measured by NT (according to *Adner et al., 2001*)  will be calculated.

The dependence of seropositivity of study participants on demographic factors (age, weight, gender) at yearly intervals from approximately 3 years (38 months) to 10 years (118 months) after the first booster vaccination will be analyzed by logistic regression at the end of the study period.

### 13.4.2 Secondary Endpoints

The antibody titers as measured by NT (according to *Adner et al., 2001*)  and ELISA at yearly intervals from approximately 3 years (38 months) to 10 years (118 months) after the first booster will be used to determine the annual decline rate.

The analysis of immunogenicity before the second booster vaccination will be carried out separately in the three age classes defined previously in Study 209. Subjects will remain in the same age class as they were assigned to at the beginning of Study 209 (1 - 2 years, 3 - 6 years, 7 - 15 years). For the analysis of immunogenicity and safety after the booster vaccination the oldest age class will be further divided into those who received FSME-IMMUN 0.25 ml Junior and those who received FSME-IMMUN 0.5 ml.

The occurrence of fever and the 95% confidence interval of the probability of occurrence will be given. The fever rate after the second booster vaccination will be categorized by severity grade.

Local and systemic reaction rates, other than fever, after the booster vaccination will be provided in tabular format, and the probabilities of the occurrence of the adverse event rates and their 95% confidence intervals will be calculated.

For each symptom queried in the Subject Diary, the number of subjects who experienced the symptom, as well as the probabilities of the occurrence and the 95% confidence interval will be given.

All AEs reported for each subject, including the same event at different time points, will be listed according to Medical Dictionary for Regulatory Activities (MedDRA) terminology.

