**Table 6.1-1**  
**Composition of TBE Vaccines**

Composition of a single dose	FSME-IMMUN 0.25 ml	FSME-IMMUN 0.5 ml
Formaldehyde-inactivated TBE virus	target 1.2 µg (range 1.00-1.38 µg)	target 2.4 µg (range 2.00 – 2.75 µg )
Origin of production virus seed	supernatant from chick embryo cells*	supernatant from chick embryo cells*
Aluminum hydroxide, hydrated	0.17 mg Al 3+	0.35 mg Al 3+
Human serum albumin	0.25 mg	0.5 mg
Sodium chloride	1.725 mg	3.45 mg
Disodium hydrogen phosphate	0.11 mg	0.22 mg
Potassium dihydrogen phosphate	0.023 mg	0.045 mg
Sucrose	max. 7.5 mg	max 15 mg
Formaldehyde	max. 2.5 µg	max. 5 µg
Protaminsulfate	max. 0.25 µg (in traces)	max. 0.5 µg (in traces)
Neomycin and Gentamicin	in traces	in traces
Water for injection	ad 0.25 ml	ad 0.5 ml

\* infected with working virus seed generated from chick embryo cells

Both FSME-IMMUN 0.25 ml Junior and FSME-IMMUN 0.5 ml are licensed for intramuscular injection. The vaccines will be administered in accordance with the Summary of Product Characteristics (SmPC): FSME-IMMUN 0.25 ml Junior is indicated for children and adolescents aged 1-15 years (until the last day before the 16th birthday) whereas FSME-IMMUN 0.5 ml has been approved for use in adults from 16 years of age (i.e. from the 16th birthday).

According to the current SmPC for FSME-IMMUN 0.25 ml Junior / FSME-IMMUN 0.5 ml, the first booster vaccination should be given at 3 years after completion of the primary vaccination series (which consists of 3 vaccinations). Subsequent booster vaccinations are recommended at 3 to 5 year intervals in children and adolescents as well as in adults up to 60 years of age.

The Sponsor will provide the Investigator with sufficient vaccine to conduct the study as well as the appropriate certificates of analysis for the investigational products.

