### **6.3 Population to be Studied**

A total of 202 healthy children, adolescents and young adults of both genders who participated in Study 700401 and received the first booster vaccination with either FSME-IMMUN 0.25 ml Junior or FSME-IMMUN 0.5 ml at 3 or 4 years after the third vaccination will comprise the subject population of the study.

The majority of subjects will be enrolled in the current study in late spring 2009 at approximately 38 months after their first booster vaccination in Study 700401 (which they received at 3 years after their third vaccination).

Those 29 subjects who were administered the first booster vaccination at 4 years after their third vaccination in Study 700401, will enter the current study in 2010. For these subjects the first visit will be shifted to take place at approximately 34 months after their first booster vaccination.

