The majority of systemic reactions (excluding fever) after all three vaccinations were mild. Systemic reactions (excluding fever) were reported most frequently in children aged 1-2 years, however, no significant difference was observed between the age groups. Headache was the most frequently reported systemic reaction, followed by restlessness (in subjects aged 1-5 years only), fatigue (in subjects aged 6-15 years only), myalgia and malaise (in subjects aged 6-15 years only).

These results confirm the consistent safety and high immunogenicity of FSME-IMMUN 0.25 ml for the vaccination of children and adolescents aged 1-15 years.

**Study 700401** was designed to investigate the seropersistence of TBE antibodies approximately 24, 34, 46 and 58 months after completion of the primary immunization schedule (3 vaccinations administered at months 0, 1 and 6 in Study 209) with FSME-IMMUN 0.25 ml in children and adolescents aged 3 to 18 years. Subjects were offered a booster vaccination at either 36, 48 or 60 months after the third vaccination with either FSME-IMMUN 0.25 ml or FSME-IMMUN 0.5 ml according to their age, depending on their individual TBE antibody levels. The antibody response was again assessed approximately 1 month after the booster vaccination. The study was completed in July 2009.

**Study 700501** aimed to investigate the seropersistence of TBE virus antibodies approximately 3 years after a booster vaccination with FSME-IMMUN 0.25 ml Junior in children who participated in Study IMAG-146A and were administered three vaccinations with either Ticovac 0.25 ml or Ticovac 0.5 ml (without HSA) during this study. Children were aged 6 months – 3 years at the time of their first vaccination. The analysis of the primary endpoint (seropositivity rate measured by ELISA and/or NT) showed that all (100%) subjects had seropositive levels of TBE virus antibodies approximately 3 years after the first booster vaccination. The results of this study confirm

the excellent immunogenicity of the primary vaccination series followed by a booster vaccination with FSME-IMMUN 0.25 ml Junior 3 to 4 years after the third vaccination.

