### 8.6.3 Description of Treatment

A second booster vaccination will be administered with either FSME-IMMUN 0.25 ml Junior or FSME-IMMUN 0.5 ml according to the subject’s age. Timing of the vaccination will depend on the level of serum TBE antibodies detected at the defined assessment time points. Subjects who may not be protected against TBE for an entire further tick season as confirmed by relatively low TBE serum antibody levels evaluated at yearly intervals from approximately 3 years (38 months) to 10 years (118 months) after the first booster (NT titer  $\leq 20$  and / or ELISA value  $\leq 126$  VIE U/ml) will be invited to receive the second booster vaccination at either the 40, 48, 60, 72, 84, 96, 108, or 120 month time point.

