### **10.3.2.2.2 Booster vaccination**

#### **BEFORE ADMINISTRATION: WARM SYRINGE TO ROOM TEMPERATURE AND SHAKE SYRINGE VIGOROUSLY FOR FIVE TO TEN SECONDS.**

The study site must have appropriate equipment and adequately trained personnel available to respond to anaphylaxis or other possibly severe acute, post-immunization adverse reactions to vaccines.

The vaccine will be given by intramuscular injection into the right or left upper arm (deltoid muscle).

Subjects will be administered either FSME-IMMUN 0.25 ml Junior or FSME-IMMUN 0.5 ml according to their age: FSME-IMMUN 0.25 ml Junior will be administered to children and adolescents up to 16 years of age and FSME-IMMUN 0.5 ml to subjects aged 16 years and older.

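### Only the oldest age class is split by second-booster product, but from Month 72 (Month 60 for 29 subjects) it is the younger classes that receive both products

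*Protocol*

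**What the plan says.** Protocol 13.4.2, repeated in the synopsis, fixes the age classes at 1-2, 3-6 and 7-15 years: "Subjects will remain in the same age class as they were assigned to at the beginning of Study 209". For results after the second booster it adds one refinement: "the oldest age class will be further divided into those who received FSME-IMMUN 0.25 ml Junior and those who received FSME-IMMUN 0.5 ml". That makes four groups: 1-2, 3-6, 7-15 Junior and 7-15 0.5 ml.

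Product is assigned by age on the day of the second booster. Protocol 6.1 states that "FSME-IMMUN 0.5 ml has been approved for use in adults from 16 years of age", with the Junior product indicated up to the day before the 16th birthday. Section 10.3.2.2.2 follows this and gives "FSME-IMMUN 0.5 ml to subjects aged 16 years and older". The second booster may be given "at either the 40, 48, 60, 72, 84, 96, 108, or 120 month time point" (Protocol 8.6.3).

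The SAP neither repeats nor replaces the oldest-class rule. Section 3.3 lists age at second booster, grouped by 0.25 mL versus 0.5 mL, as a baseline variable. Sections 5.2.2.2, 5.2.2.3 and 5.2.3 present post-booster GMT/GMC, fold rise and seropositivity by year and combined. Section 6.3 gives counts and percentages for adverse events. None of these four sections names a product split.

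**The concern.** A class fixed at the first Study 209 dose grows older while the product boundary stays at the 16th birthday, so the class that straddles the boundary changes over the schedule. A rule that splits one named class can be right for only part of the follow-up.

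Response to the second booster, and its safety, are the two secondary objectives. If a class contains recipients of both products and is reported whole, its GMT, fold rise, seropositivity rate or reaction rate averages over two antigen contents (target 1.2 and 2.4 µg). The mix also changes with booster year, so a trend across years within a class could reflect product, time since the first booster, or both. Presentation by year separates the products only at visits where the class is single-product. The combined column pools them.

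**Working it through.** **Inputs**
- First to third Study 209 dose: 0.5 year ("3 vaccinations administered at months 0, 1 and 6 in Study 209", Protocol 6.4.2).
- Third dose to first booster: "first booster vaccination in Study 700401 at 3 or 4 years after the third vaccination in Study 209" (Protocol 13.1). The 4-year cohort is "Those 29 subjects who were administered the first booster vaccination at 4 years after their third vaccination in Study 700401" (Protocol 6.3).
- First to second booster: the listed months, with 36 replacing 40 for the 4-year cohort (Protocol 10.3.2.2, footnote).
- Classes in completed years: [1,3), [3,7) and [7,16).

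**Check on the age arithmetic.** Study 700401 is described as covering ages 3 to 18, with its first blood draw about 24 months after the third dose. The sum gives 1 + 0.5 + 2 = 3.5 and just under 16 + 0.5 + 2 = 18.5, that is 3 to 18 completed years. This agrees.

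**Formula.** Age at second booster = Study 209 age + 0.5 + 3 (or 4) + t/12. A subject is therefore due 0.5 ml if the Study 209 age is at least
- 16 − 3.5 − t/12 in the 3-year cohort;
- 16 − 4.5 − t/12 in the 4-year cohort.

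A class receives both products when this threshold lies strictly inside it.

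**3-year cohort**

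| Month | Threshold (years) | 1-2 class | 3-6 class | 7-15 class |
|---|---|---|---|---|
| 40 | 9.17 | Junior | Junior | both |
| 48 | 8.5 | Junior | Junior | both |
| 60 | 7.5 | Junior | Junior | both |
| 72 | 6.5 | Junior | both | 0.5 ml |
| 84 | 5.5 | Junior | both | 0.5 ml |
| 96 | 4.5 | Junior | both | 0.5 ml |
| 108 | 3.5 | Junior | both | 0.5 ml |
| 120 | 2.5 | both | 0.5 ml | 0.5 ml |

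**4-year cohort (29 subjects).** The thresholds are 8.5, 7.5, 6.5, 5.5, 4.5, 3.5, 2.5 and 1.5 at Months 36, 48, 60, 72, 84, 96, 108 and 120. The 7-15 class is mixed at Months 36 and 48 only, the 3-6 class at Months 60 to 96, and the 1-2 class at Months 108 and 120.

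**Visit windows.** Every threshold is at least 0.5 year from a class boundary. The stated windows are 14 days on the third dose plus 30 or 60 days on Visit 4, that is 44/365 = 0.12 or 74/365 = 0.20 year, so they cannot change the pattern. The window on the first booster is not given. Even taking the wider total throughout, it would have to exceed 0.5 − 0.20 = 0.3 year to matter.

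**Share due 0.5 ml if boosted at that visit.** The documents do not give the age distribution within class, so this part is an assumption. With u = (threshold − lower limit)/(class width), uniform ages give 1 − u. Densities falling or rising linearly across the class give (1 − u)² and 1 − u².

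| Class, cohort, month | u | Uniform | Range |
|---|---|---|---|
| 3-6, 3-year, 72 | 0.875 | 12.5% | 1.6-23.4% |
| 3-6, 3-year, 84 | 0.625 | 37.5% | 14.1-60.9% |
| 3-6, 3-year, 96 | 0.375 | 62.5% | 39.1-85.9% |
| 3-6, 3-year, 108 | 0.125 | 87.5% | 76.6-98.4% |
| 1-2, 3-year, 120 | 0.75 | 25% | 6.3-43.8% |
| 1-2, 4-year, 108 | 0.75 | 25% | 6.3-43.8% |
| 1-2, 4-year, 120 | 0.25 | 75% | 56.3-93.8% |

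**The case against.** The SAP may already go part of the way. Its Section 3.3 dose-level variable covers every class, and Section 5.2.2.4 draws on the age groups in Section 3.3 for the distribution curves, so Section 3.3 categories can serve as reporting strata. The SAP's post-booster text names no age class at all, so a mixed 3-6 result appears only if the Protocol rule is carried into the tables. Those are prepared separately and are not among the documents. This limits what can be said about the final report. It does not supply the missing statement, because no SAP text shows post-booster results by product.

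Two points narrow the finding. Within a cohort only one younger class is mixed at any visit, and the 1-2 class is mixed only at Month 120, or at Months 108 and 120 among the 29. Also, splitting the 7-15 class at later visits merely leaves an empty column. Pooled over visits that class still holds both products, so its split should stay.

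The study is descriptive, the results concerned are secondary, and the yearly persistence estimates are untouched. That bears on priority, not on whether the rule fits the schedule. The Protocol gives no reason for its split; that it was meant to keep the products apart is an inference, though the natural one.

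**Conclusion.** The concern holds. In the 3-year cohort the rule fits the visits to Month 60, when only the 7-15 class spans age 16. From Month 72 (Month 60 for the 29 subjects) it splits a class that is single-product at those visits. It leaves whole the 3-6 class, mixed at four visits in each cohort, and the 1-2 class, mixed at one visit in the 3-year cohort and two in the 4-year cohort. Over the full schedule six class-by-product groups can arise, and the rule provides four.

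Which class-months are mixed does not depend on any assumed age distribution, provided each class spans its stated ages. The percentage shares do, and they describe whole classes rather than subjects actually boosted. The documents give no counts boosted by class, visit and product, so the number affected is unknown and the 1-2 class 0.5 ml group may be small or empty. This should be corrected, but it does not touch the seropersistence results. It concerns the grouping of results only, not which product any subject should receive.

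**What to change.** In Protocol 13.4.2 and the synopsis, replace the oldest-class split with a split by product received (0.25 ml Junior or 0.5 ml) in every Study 209 age class in which both were given, and add an overall summary by product. State the same grouping in the SAP for post-second-booster GMT/GMC (5.2.2.2), fold rise (5.2.2.3), seropositivity (5.2.3) and adverse events (6.3).

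The cost is wording and extra table columns from data already recorded. Some cells will be small, since 179 subjects were enrolled (SAP 2.2.2) and are divided by class, product and year. Amending the Protocol brings the ethics committee review described in Protocol 16.2. If no amendment is otherwise planned, stating the grouping in the SAP would be enough to govern the tables.
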